9.3.1 General Considerations

All imputed values will be determined prior to database lock and conducting primary analyses via rules documented prospectively in the final Statistical Analysis Plan for the study.

Deceased participant will score 6 on the mRS, 42 on the NIHSS and 0 on Barthel Index and be counted as non-responders. Every effort will be made to keep missing data, particularly the Day 90 outcome assessments, to a minimum.

For the primary analysis, for participants who are missing the mRS at Day 90:

- if the participant is known to be dead at Day 90, they will be considered to be a non-responder and the mRS will be imputed as 6
- if the mRS was obtained at the Day 30 assessment or later, it will be carried forward as the Day 90 mRS value
- if both the Day 30 and Day 90 mRS scores are missing but the participant is documented to be alive at Day 90 they will be considered to be a non-responder and the mRS will be imputed as a 5
- if both the Day 30 and Day 90 mRS scores are missing and the mortality status of the participant is unknown at Day 90 they will be considered to be a non-responder and the mRS will be imputed as a 6.

If more than 5% subjects randomized are missing the mRS score at Day 90, additional imputation methods will be employed- details of which will be included in the SAP.

For the secondary analysis of rate of mortality, for participants for whom the morality status is not known at Day 90:

- if they were alive at Day 30, then the subject will be imputed as alive at Day 90
- If both the Day 30 and Day 90 mortality is status is missing, the participant will be imputed as Dead at Day 90.

For other analyses involving the mRS (other than mortality), the same imputation approach will be taken as for the primary analysis. No imputation will be done on the missing one-year follow-up mortality data.

A number of events may occur after study drug initiation and during the 90-day trial observation period that could impact data completeness, the interpretation of, or the ability to observe, each outcome variable. Details of handling of such events, which may or may not meet the ICH definition of intercurrent events (IEs)⁴², will be provided in the SAP.

Participants who are missing NIHSS or BI endpoint data at Day 90 will have the last recorded score carried forward, provided that this score was obtained at the Day 30 visit or later. Otherwise, the missing NIHSS or BI will be imputed to the median score obtained at Day 90 in the trial.

Sensitivity analyses using various imputation techniques will be specified prospectively in the SAP before the database lock for the interim analysis if more than 5% of participants randomized are missing the primary endpoint.

Unless otherwise noted, categorical data will be summarized for each treatment group using counts and percentages, with the denominator for percentages being the number of participants in the population of interest. Unless otherwise noted, continuous data will be summarized for each treatment group using the number of observations (n), mean, standard deviation (SD), median, minimum, and maximum. Some continuous data will be reported as the median, interquartile range (IQR), minimum and maximum according to the clinical meaning of the data.

Percentages will be rounded to one decimal place, except 0% and 100% will be displayed without any decimal places. Minima and maxima will be rounded to the precision of the original value; means and medians will be rounded to one decimal place greater than the precision of the original value; SDs will be rounded to two decimal places greater than the precision of the original value. P-values will be reported to four decimal places (0.xxxx), with values less than 0.0001 presented as <0.0001.

Inferential analyses will generally include statistics such as 2-sided 95% confidence intervals (CI), and p-values. Unless stated otherwise, all statistical tests will be one-sided 0.025 (2-sided 0.05).

In order to avoid sparse sites (sites with fewer than 10 randomized participants) sites within a geographic region (Canada/USA/Rest of World) with fewer than 10 randomized participants will be pooled into a single pooled site for use in efficacy analyses.

The software used for all summary statistical analyses will be SAS[®] (SAS Institute, Inc.) version 9.4 or later.

9.3.2 Efficacy Analysis

The primary and secondary efficacy estimand analyses will be conducted on the intent-to-treat (ITT) population, defined as all participants randomized into the trial with grouping by randomized treatment, regardless of treatment actually received. Two additional analyses to the primary analysis will be conducted: (1) the primary analysis reapplied to the Per Protocol population; (2) a re-randomization analysis to demonstrate that minimization did not bias the primary endpoint analysis.

In order to protect the overall trial false positive rate, the primary efficacy estimand analysis and secondary efficacy estimand analyses will be analyzed in a fixed sequence, stopping and calling all subsequent analyses exploratory (and accepting the null hypothesis) at the first failed hypothesis test in the sequence. The fixed sequential order is:

- 1) Primary efficacy estimand analysis.
- 2) Secondary efficacy estimand analyses, as specified in the order presented in Table 9-1 below.

Endpoint	Statistical Analysis Methods
Primary	Overall proportion participants experiencing a favorable functional outcome 90-days post-randomization, defined as 0 to 2 on the mRS.
	The pivotal primary analysis will be conducted on the ITT population at the one-sided 0.025 (2-sided 0.05) significance level overall (for the trial), adjusted for the interim analysis per the O'Brien-Fleming boundary spending function. It will use the method of Ge et al, 2011 ⁴⁰ . The proportion difference in responder rate between two treatment groups and the associated standard error and 95% confidence interval will be reported. P-value for the primary endpoint will be calculated based on the estimates reported by the Ge et al, 2011 ⁴⁰ method.
	The pivotal primary analysis model will be a logistic regression model with fixed effects including the treatment group, the stratification covariate of time from stroke onset to randomization ≤ 4.5 hours (yes/no) and the randomized minimization factors (age, baseline NIHSS score, occlusion location, time from qualifying imaging to randomization, baseline ASPECT score, sex, and pooled site), and an interaction term of treatment by time from stroke onset to randomization. If the interaction term is not significant at the level of 0.05, it will be removed from the model. The odds ratios along with the 95% CI will be reported in addition to the primary Ge et al, 2011 method results. If the interaction term is significant, results will be also reported by randomization stratum separately, using the Ge et al, 2011 method.

Table 9-1: Statistical Analysis Methods

	The secondary analysis in support of the primary analysis will be the two sample proportion Wald test. The risk difference along with the estimated standard error, 95% CI and the Wald test statistics will be reported.
	An additional analysis will be conducted in which the primary analysis is reapplied to the per protocol population with observed cases only.
	Three separate efficacy analysis timepoints are planned for this trial. The first analysis will be at the interim analysis planned at 60% information on the primary endpoint. The second analysis timepoint will be based on the completion of Day 90 visits for the main trial. The third analysis will be following the completion of the 1-Year follow up.
Secondary	The secondary endpoints with binary outcomes (mortality rate, worsening of stroke and NIHSS responder) will be assessed via the same analysis as the primary analysis (i.e, the logistic regression based, with the odds ratios along with the 95% CI and two sample proportion test) All tests will be conducted with one-sided significance level of 0.025 (2-sided 0.05). A fixed sequence multiple testing procedure will control the overall experiment-wise error rate for the trial (see below). It pre-specifies that, with all tests conducted at the same pre-specified significance level, the primary endpoint will be tested first, and all subsequent tests are considered failed and deemed exploratory if conducted as part of the fixed sequence testing sequence provided that the proportional odds assumption is found to be valid on testing. If it is found to be invalid, the remaining secondary endpoints will be deemed to analyzed in the fixed testing sequence specified without the mRS shift analysis; i.e. it will be removed from the fixed sequence testing sequence. Mortality rates, defined as the number of deaths observed divided by the number of participants observed over the 90-day study period, will be additionally supported using time-to-death survival function analysis, both unadjusted shown using Kaplan-Meier analysis and adjusted via Cox proportional hazards regression.
	Worsening of Stroke is determined as the number of participantsexperiencing at least one worsening of stroke divided by the number ofparticipants observed over the 90-day period in that treatment group, betweennerinetide and placebo control participants. Results will be summarized andtabulated.
	"mRS shift analysis" The primary analysis of the ordinal mRS scores will employ a proportional odds model (POM) to test the hypothesis that, among randomized subjects, those who are treated with nerinetide will show a shift in their mRS score distribution at 90 days relative to the mRS distribution of the placebo subjects. The magnitude of the shift will be estimated as the common
ESCAPE-NE	XT

	odds ratio (95% CI). Modified Rankin scores of 5 and 6 (bed-bound with severe disability, and death) will be collapsed into a single category representing severely limited functioning. An adjusted POM will be used to derive the common odds of improvement (i.e. the nerinetide vs. placebo "shift" in mRS score distributions). Adjustment of the treatment effects will include the same set of variables as used for the logistic regression model for the primary estimand. Deceased participants will be included with a mRS score of 6.
	Since the analysis of the ordinal mRS scores will employ a proportional odds model (POM), if test of the proportional odds assumption shows the assumption to be invalid, this secondary analysis will be removed from the fixed sequence testing procedure and conducted as an exploratory analysis instead.
	NIHSS scores at Day 90 will be dichotomized into 0-2 (indicating a good neurological outcome) versus >2 (indicating otherwise). Deceased participants will be included with a NIHSS score of 42. The proportion of participants achieving a good neurological outcome at Day 90 in nerinetide versus placebo control participants will be analyzed. Results will be summarized and tabulated.
Tertiary	Total volume of new strokes on MRI or CT brain imaging in the nerinetide versus placebo control participants. Total volume will be assessed using an unadjusted two-tailed Student's t-test and supported by an adjusted analysis comprising of a linear regression that includes the stratification and minimization variables. A cubic root transformation will be performed if needed. Results will be reported with confidence intervals for the unadjusted and adjusted treatment effect between treatment groups.
	Barthel, Day 90 mRS≤1, Day 90 mRS 4-6 , the tertiary outcomes comprising proportions of responders will be analyzed similarly to the primary efficacy analysis. Deceased participants will be included in the ITT population with a Barthel Index score of 0.
	EQ-5D-5L will be assessed descriptively. Results will be summarized and tabulated.
Exploratory	Exploratory subgroup analyses will be conducted to determine whether any of these factors can modify the effect of the nerinetide vs. placebo treatments. Sub-group analyses will be performed on the primary outcome and include forest plots to display effect sizes by sub-group ⁶ .
	 Dichotomous sub-groups of interest include the following: Time from stroke onset to randomization (≤4.5 hours vs. > 4.5 hours) Age (<80 years vs ≥ 80 years of age) Age (<65 years vs ≥ 65 years of age) Sex (men vs. women)

• Ethnicity (Hispanics vs non-Hispanic)
• Race (White, Asian, Black, Other)
• Baseline stroke severity (NIHSS > Median vs. NIHSS <= Median)
Baseline occlusion location (MCA vs. ICA)
• Baseline ASPECT score (5-7 vs. 8-10)
• Time from qualifying imaging to study drug initiation (greater than vs. less than the median).
• Time from onset of stroke symptoms to start of study drug (greater than vs. less than the median).
• Degree of reperfusion (TICI 2b-3 vs. TICI <2b)
• Subjects weighing between 105-120 kg. vs. \leq 105 kg.
• Subjects receiving a thrombolytic treatment post-randomization vs. those that do not.
• Subjects diagnosed with COVID-19 infection while in the acute care hospital or known to have active COVID-19 infection at presentation vs. those that do not.
• Subjects who received a thrombolytic as a rescue medication vs. those that do not
• Subjects in whom there was a reported AE of recurrent stroke vs. those in who there was not
Additional sub-groups may be examined.
Sub-group analysis results will also be reported by randomization strata if the interaction term in the primary pivotal analysis plus the treatment-by-stratification interaction term is significant at the 0.05 level in the adjusted logistic regression of the primary analysis.

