9 STATISTICS

9.1 Sample Size Determination

The primary estimand will be the adjusted difference in the mRS response (i.e., mRS score of 0-2) proportions between treatment conditions (nerinetide vs. placebo) in the target patient population at Day 90. Participants with mRS score of 0-2 are defined to be responders. Deaths occurring over the Day 90 period will be considered as non-responses.

Primary hypothesis test and 95% confidence interval estimate for the primary estimand will be provided by the analytic method of Ge, 2011^{40} discussed in FDA's most recent draft guidance Adjusting for Covariates in Randomized Clinical Trials for Drugs and Biological Products⁴¹, adjusting for the stratification covariate of time from stroke onset to randomization ≤ 4.5 hours (yes/no) and the randomized minimization factors (age, sex, baseline NIHSS score, baseline ASPECT score, occlusion location, time from qualifying imaging to randomization and pooled site), and an interaction term of treatment by time from stroke onset to randomization. If the interaction term is not significant at the level of 0.05, it will be removed from the model.

Up to 850 male and female participants aged 18 or older harboring AIS and who are selected for endovascular revascularization without intravenous or intra-arterial thrombolytic therapy will be enrolled.

Based on results of ESCAPE-NA1 and assuming a 50% overall responder rate for the placebo group, there will be approximately 91.3% power to detect an 11.4% absolute effect difference between response rate (proportion of responders, with Day 90 mRS in the range 0 to 2) with nerinetide and placebo, at alpha level 0.025 one-sided (0.05 2-sided), using the planned sample size of 850 evaluable subjects, randomized 1:1, per group [EaST v6.5, 2022].

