This sample size was calculated taking into account a dropout/non-evaluable rate of 2% with a lag to primary endpoint assessment of 4 months, estimated accrual rate of 50 participants per month, target effects 0.5 vs 0.6114 and a single interim analysis for early superiority stopping with an O'Brien-Fleming alpha spending function boundary at 60% information (510 evaluable participants). The interim analysis is planned to take place at 60% information (primary endpoint), i.e. when approximately 510 of the target 850 patients have reached their primary endpoint assessment. The cumulative alpha spent at the interim analysis is 0.004 and final analysis 0.025, one-sided (0.05 2-sided); the stopping boundaries on the Z scale are 2.668 (interim) and 1.981 (final) and on the p-value scale 0.004 (interim) and 0.021 (final), all on the assumption that the interim is conducted at 60% information.

See Section 9.4 for further details on the interim analysis.

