8.4 Handling of Enrollment Overage

The interim analysis is anticipated to take place once 510 participants have reached their 90 day follow-up. The IDMC may recommend to (1) stop the trial due to overwhelming efficacy (2) to complete enrollment to the originally-planned 680 participants or (3) to increase the sample size based on the results of the sample-size re-estimation up to 1020 participants.

It is possible that, by the time the IDMC provides a recommendation, enrollment in the study could exceed the number of participants needed to adhere to the IDMC recommendation. In such an eventuality, the primary outcome variable analysis for the main study and for the 1-Year Sub Study, as well as the Secondary Efficacy Estimand Analyses for the Main Study and for the 1-Year Sub Study may also be performed on the participants as per the IDMC-recommended sample size as needed.

•

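### The interim look adjusts the test boundary but not the reported estimate or 95% CI, so an early stop would on average overstate the effect

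*Combined protocol and SAP*

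**What the plan says.** **Decision rule.** Protocol 9.1 and 9.4 plan one efficacy look at 60% information (510 of 850) and state that "the stopping boundaries on the Z scale are 2.668 (interim) and 1.981 (final"). Table 9-1 says that the significance level is adjusted through the O'Brien-Fleming spending function. SAP 4.1 says that the type I error and the final efficacy boundary will follow the alpha actually spent.

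**Reported result.** Table 9-1: "The proportion difference in responder rate between two treatment groups and the associated standard error and 95% confidence interval will be reported". Protocol 9.3.1 and SAP 4.1 set two-sided 95% intervals as the general convention. SAP 6.1.3 reports a relative risk with a 95% CI, plus a bootstrap 95% CI for the unconditional effect. Neither document mentions a repeated or stagewise interval, a median-unbiased estimate, or any other correction for stopping.

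**Overrun.** SAP 8.4 foresees enrolment passing the number that the IDMC recommends. It then says that the primary and secondary analyses "may also be performed on the participants as per the IDMC-recommended sample size as needed". No trigger is given, and nothing says how this analysis ranks beside the ITT result.

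**Two designs.** SAP 1.4 and 8.1 describe a look at 75% of 680, boundaries of 2.34 and 2.012, and re-estimation up to 1020. Protocol 9.3 gives the SAP precedence where the two differ.

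**The concern.** A trial that stops early does so because its interim estimate was high. The estimate at that moment is therefore biased upward, and an ordinary 95% interval is centred on the biased value. If the design assumption is right, an early stop is nearly an even chance, so this is a main scenario. Nothing in the plan would correct or flag the inflation.

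There is a smaller mismatch at the final look. The test needs Z of at least 1.981, while the reported interval excludes zero from 1.960. A reader could then see an interval that excludes zero beside a failed primary test. After a stop, an optional second analysis of the primary outcome with no stated rank adds an avoidable choice once the data are unblinded.

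**Working it through.** **Inputs, all from protocol 9.1.**
- Alpha: "at alpha level 0.025 one-sided (0.05 2-sided").
- Placebo rate: "assuming a 50% overall responder rate for the placebo group".
- Effect and power: "approximately 91.3% power to detect an 11.4% absolute effect difference". The calculation itself uses "target effects 0.5 vs 0.6114", which is 11.14 points.
- Size: "using the planned sample size of 850 evaluable subjects, randomized 1:1, per group", read as 425 per arm because enrolment is capped at 850.
- Accrual of 50 per month and a 4-month lag: 50 × 4 = 200 more randomized by the time 510 reach the endpoint.

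**Step 1: reproduce the design.** With spending function α(t) = 2[1 − Φ(z₀.₉₈₇₅/√t)], α(0.6) = 0.0038, which gives Z = 2.669. Solving the bivariate normal with correlation √0.6 gives a final Z of 1.981. Power is 90.6% (N = 850, 0.6114), 91.8% (850, 0.614) and 91.3% (850 × 0.98 = 833, 0.614). The plan's figures reproduce. The stated final p of 0.021 is the alpha increment 0.025 − 0.004, whereas the one-sided tail at 1.981 is 0.0238. I use the Z value.

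**Step 2: estimate after an interim stop** (unadjusted, true d = 0.1114).
- SE at 510 = √[(0.5×0.5 + 0.6114×0.3886)/255] = 0.0437. Drift = 0.1114/0.0437 = 2.548.
- P(stop) = 1 − Φ(2.668 − 2.548) = 0.452.
- E(estimate | stop) = d + SE·φ(0.120)/[1 − Φ(0.120)] = 0.1114 + 0.0383 = 0.1497. That is 15.0 points, about 34% above the truth.
- With 200 overrun participants: (510×14.97 + 200×11.14)/710 = 13.9 points.

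The same formula for other true effects, protocol boundary:

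| True effect | P(stop) | Mean at stop, n = 510 |
|---|---|---|
| 5 | 6% | 13.7 |
| 8 | 20% | 14.2 |
| 9.6 | 32% | 14.5 |
| 11.14 | 45% | 15.0 |

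For a true 11.14 points, an assumed 10% variance reduction from covariate adjustment (not in the documents) gives 14.4. The SAP boundary of 2.34 at 510, without a sample size increase, gives a 58% stop probability and a mean of 14.1.

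**Step 3: interval against test at the final look.** With 425 per arm and a 50% placebo rate, the 95% CI excludes zero from 6.69 points, but the test passes only from 6.76. Example: an observed 6.73 points has SE 3.41 and Z = 1.970. The lower limit is +0.04 with 1.960 SE and −0.04 with 1.981 SE. The probability of no early stop and a final Z between 1.960 and 1.981 is 0.12% under the null, 0.71% at 5 points, 0.75% at 8 and 0.34% at 11.14. With the SAP bound of 2.012 it is 1.2 to 1.8% for true effects of 5 to 11 points.

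**Step 4: coverage over all trials.** Simulated coverage of the plain CI is about 94.5 to 94.9%. At a true 5 points it lies wholly above the truth 3.4% of the time (nominal 2.5%), or 2.9% if overrun participants are included.

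**The case against.** Three replies have force.

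1. **Error control is intact.** The test is adjusted, so a CI that narrowly excludes zero changes no decision. This stands; the mismatch is a reporting inconsistency.

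2. **The overrun softens the bias.** ITT is all randomized participants (protocol 9.2, SAP 2.1), and the first report follows completion of Day 90 visits (protocol 4.1 and 4.5). On the plain reading, overrun participants are already in the headline analysis. Averaged over all trials with the overrun included, the mean estimate is 11.35 against a true 11.14, and coverage is 95.0%. This stands for the unconditional picture. Among stopped trials the mean is still 13.9.

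3. **The analysis set is specified.** A reader might infer from SAP 8.4 that the primary set is left open. The documents do not support that: the wording adds an analysis and does not replace ITT. The gap is the missing trigger and rank.

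A reader might also infer that any early stop must report more than the design effect, because the smallest unadjusted difference that crosses 2.668 on 510 participants is 11.65 points. That needs a placebo rate near 50%, no covariate adjustment, exactly 510 participants and the protocol boundary. The pivotal analysis is covariate-adjusted: a variance reduction of 4.4% lowers the threshold to 11.4, and 8.8% lowers it to 11.14. Under the SAP boundary it is 10.25. With overrun participants included, about 17% of stopped trials report below 11.4 when the truth is 11.4.

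**Conclusion.** The concern holds as a gap in estimation and reporting. For a true 11.14 points under the protocol boundary, 45% of trials stop early with a mean estimate of 15.0 points on 510 participants, or about 13.9 on 710. The upward bias persists under covariate adjustment, under the SAP boundary and after overrun; only its size changes. The interval-test mismatch affects about 0.1 to 0.8% of trials under the protocol boundary and does not touch type I error.

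The figures rest on a 50% placebo rate, an unadjusted risk difference, a look at exactly 510, and 200 overrun participants. The documents do not support saying that an early stop must exceed the design effect, or that the primary analysis set is undefined.

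**What to change.** First reconcile the two designs, since the multipliers depend on which boundary applies and the SAP currently prevails. Then:

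1. **Final analysis.** Report the CI with the final boundary multiplier actually in force: 1.981 SE under the protocol (a 95.24% interval) or 2.012 SE under the SAP (95.58%), recalculated if the interim timing differs.
2. **After an interim stop.**
   - Give the boundary-matched interval on the interim data set only (2.668 SE, or 2.34 SE under the SAP), as the companion to the confirmatory test.
   - Show the ITT estimate including overrun participants with its own interval, from a method that allows for the overrun. Do not carry the interim multiplier over: 2.668 SE on about 710 participants would include zero in about 6% of stopped trials at 11.14 points and 30% at 5 points.
   - Name a bias-adjusted estimate and CI, for example median-unbiased under stagewise ordering, and print it beside the naive one.
3. **SAP 8.4.** Label the analysis on the IDMC-recommended number as supportive.

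**Cost.** SAP wording and a few lines of code. The final CI is wider by 1.981/1.960 (about 1%) or 2.012/1.960 (about 3%). After an early stop, the interim interval is about 36% wider under the protocol (2.668/1.960) and the adjusted estimate is less favourable. Fixes 1 to 3 change no boundary, sample size or power.

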6.8.1 Rescue Medicine/Treatment

6.8.1.1 Early Study Drug Cessation

The intervention is the intravenous administration of 2.6 mg/kg (up to a maximum of 270 mg) of nerinetide over a 10 ± 1 minute intravenous infusion to participant undergoing endovascular mechanical thrombolysis/thrombectomy. It is expected that dosing will be completed before the endovascular procedure is completed. However, if dosing is ongoing during the endovascular procedure, dosing will not be stopped in the event of an adverse intra-procedural event deemed to be a complication of the endovascular intervention.

The investigator may terminate drug administration at his/her discretion.

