8.3.1 Time Period and Frequency for Collecting AE and SAE Information

All SAEs will be collected from the start of study drug administration until Day 90, in addition SAE assessed as related to study drug, or have a fatal outcome will be collected to Day 90, see the Schedule of Activities.

All AE will be collected from the start of study drug administration until Day 30 at the time points specified in the Schedule of Activities.

Medical occurrences that begin before the start of study intervention but after enrolment into the trial will be recorded on the Medical History section of the electronic case report form (CRF) not the AE section.

All SAEs will be recorded and reported to the sponsor or designee immediately, without undue delay, under no circumstances later than 24 hours following the knowledge of such an event, as indicated in Appendix 3. The investigator will submit any updated SAE data to the sponsor within 24 hours of it being available.

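### Protocol Table 9-1 lists variables known only after randomization as effect modifiers, and within those groups the comparison of arms is not protected by randomization

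*Combined protocol and SAP*

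**What the plan says.** The Exploratory row of protocol Table 9-1 (section 9.3.2) states its purpose: "Exploratory subgroup analyses will be conducted to determine whether any of these factors can modify the effect of the nerinetide vs. placebo treatments". The analyses are on the primary outcome and are shown in forest plots.

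Most of the listed factors are fixed at baseline. These are not:

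- "Subjects in whom there was a reported AE of recurrent stroke vs. those in who there was not"
- "Subjects receiving a thrombolytic treatment post-randomization vs. those that do not"
- "Subjects who received a thrombolytic as a rescue medication vs. those that do not"
- "Degree of reperfusion (TICI 2b-3 vs. TICI <2b"
- "Subjects diagnosed with COVID-19 infection while in the acute care hospital or known to have active COVID-19 infection at presentation", against those without. This mixes status at arrival with a later diagnosis.

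The protocol attaches no caveat and no causal method to these rows. Protocol 9.3.1 leaves the handling of events after dosing to the SAP, and SAP 4.2 names only death as an intercurrent event.

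SAP 6.4 has its own list. It keeps the TICI row, omits the recurrent-stroke, thrombolytic and COVID-19 rows, and allows further subgroups. It fits a separate logistic model in each subgroup, adjusted for the stratification and minimization variables. Protocol 9.3 says the SAP prevails where the two differ.

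**The concern.** A subgroup effect can be read as effect modification only if group membership was settled before allocation. If treatment can change membership, the treated and placebo patients in the group are different kinds of patient, and part of the difference between them is selection. Adjusting for baseline covariates, as SAP 6.4 does, does not repair this unless those covariates capture all the prognosis shared by the grouping event and the outcome.

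At stake is the reading of the forest plot. Rows of this kind would sit next to valid baseline subgroups, in the same format and under the same stated purpose. A reader could take a selection artefact for evidence that the drug works better or worse in some patients.

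**Working it through.** **Step 1. When does each variable become known?**

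- *Recurrent-stroke AE.* Protocol 8.3.1: "All AE will be collected from the start of study drug administration until Day 30". It cannot be known at randomization. Three further features follow from the documents. Randomized but undosed patients cannot have such an AE. Patients who die early have less time to have one. AE collection ends at Day 30 while SAE collection runs to Day 90.
- *Thrombolytic after randomization, and rescue thrombolytic.* The first is post-randomization by its own words. For the second, protocol 5.2 excludes a plasminogen activator in the 24 hours before randomization.
- *TICI.* Protocol 5.2 excludes patients whose procedure is already complete, and protocol 6.8.1.1 says "It is expected that dosing will be completed before the endovascular procedure is completed". Table 9-1 does not say which reading is used. I take it to be the final grade, which is reached after randomization.
- *COVID-19.* Status at presentation is baseline; in-hospital diagnosis is not.
- *Two time-to-study-drug rows.* These end at the start of infusion, just after randomization, but mostly measure earlier delay. I do not count them.

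**Step 2. Could treatment change the variable?**

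- *Recurrent stroke: plausible.* Protocol 2.1.5 reports that in ESCAPE-NA1, without alteplase, there were fewer neurological SAEs on nerinetide, with ischemic stroke among the types named. That is a pooled group of events, not recurrent stroke alone.
- *TICI and thrombolytic use: not shown.* Protocol 2.1.2 and 4.3 say the drug has no fibrinolytic activity and does not affect thrombolytics, and treatment is blinded (6.3).

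**Step 3. How large could it be?** The plan gives no recurrence rate and no figure for these rows, so there is nothing to reproduce. The following is illustration only. Apart from the protocol's 50% placebo responder rate, every input is assumed.

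Let *q* be the recurrence risk on placebo, *r* the fraction of those recurrences that still occur on drug, *x* the responder rate in preventable cases and *y* the rate in non-preventable ones. Suppose the drug changes nobody's mRS response, so the true effect is zero everywhere.

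- With the event: placebo = r·y + (1−r)·x; drug = y; difference = (1−r)(y−x).
- Without the event: placebo p = [0.5 − q(r·y + (1−r)·x)]/(1−q); drug = [(1−q)p + q(1−r)x]/(1−q·r).

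*Strong case* (q = 0.10, r = 0.5, x = 0.35, y = 0.10):
- With the event: 0.5 × (0.10 − 0.35) = −0.125.
- Without: placebo (0.5 − 0.0225)/0.90 = 0.5306; drug (0.4775 + 0.0175)/0.95 = 0.5211; difference about −0.0095.

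*Mild case* (q = 0.05, r = 0.75, x = 0.40, y = 0.20):
- With the event: 0.25 × (0.20 − 0.40) = −0.05.
- Without: placebo 0.4875/0.95 = 0.5132; drug (0.4875 + 0.005)/0.9625 = 0.5117; difference about −0.0015.

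*No effect on recurrence* (r = 1): both differences are 0.

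A softer model was simulated with 4,000,000 patients per scenario. A standard normal severity factor U raises recurrence risk (log-odds slope 1) and lowers response. The response logit is 0.1 − U − 1.5 × event, with no direct drug effect.

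| Placebo recurrence | Reduction on drug | With event (points) | Without event (points) |
|---|---|---|---|
| 5% | 40% | −0.29 | −0.39 |
| 5% | 50% | −0.53 | −0.46 |
| 10% | 40% | −0.79 | −0.67 |
| 10% | 50% | −0.63 | −0.86 |

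With no reduction, the simulated differences lay between −0.06 and +0.10 points, which indicates the simulation noise.

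**Step 4. Precision of the row.** With 850 patients and 5% or 10% recurrence in both arms, each arm contributes 850 × 0.05/2 = 21.25 or 850 × 0.10/2 = 42.5 patients. At an assumed 20% responder rate, the 95% half-width is 1.96 × √(2 × 0.2 × 0.8/m), which is 24.1 points for m = 21.25 and 17.0 points for m = 42.5.

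**The case against.** The strongest reply has four parts.

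*These analyses decide nothing.* They are labelled exploratory and lie outside the fixed testing sequence. This stands, and it limits the weight of the point. The label deals with multiplicity, however, not with comparability of the arms.

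*The governing document already omits most of these rows.* This is correct as the texts now read: of the rows above, SAP 6.4 keeps only TICI. It is not a full answer. That SAP is based on protocol V5.0 and describes an initial target of 680 with re-estimation up to 1020, whereas the protocol now plans 850. It also leaves the list open, so a revision could carry the rows across.

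*Bias is conditional.* This stands. A reader might infer that all these rows are biased, or that both recurrent-stroke groups would show apparent harm. The documents support neither. Bias requires an effect of treatment on the grouping variable, and any simulated harm depends on assumed inputs. A reader might also equate recurrent stroke with the worsening endpoint. Protocol 8.1.3 defines that endpoint by the index stroke, so a recurrent stroke is a different event.

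*The thrombolytic rows have a reason to exist.* Cleavage of nerinetide by plasmin is the rationale for the trial population (protocol 4.2 and 4.3). This stands, and it argues for showing those data separately rather than deleting them.

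**Conclusion.** The point holds as a matter of structure. Four rows of Table 9-1 depend wholly, and the COVID-19 row partly, on information that arises after randomization, yet they are planned as effect modifiers. Comparisons of arms within them are not randomized comparisons.

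Whether they are biased depends on treatment affecting the grouping variable. That is plausible for recurrent stroke and undemonstrated for TICI and thrombolytic use. The size cannot be derived from the documents. Under the assumed inputs, the distortion in the recurrent-stroke group runs from about 0.3 to 12.5 points, and in its complement it stays below about 1 point. In the recurrent-stroke group it would be smaller than the sampling error of the row.

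Sample size, power, alpha and the primary estimate are unaffected. This is a low-severity matter of labelling and presentation.

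**What to change.** 1. Limit the effect-modifier forest plot to variables fixed before randomization. For COVID-19, use status at presentation only.
2. Take the recurrent-stroke AE out of the subgroup list and report it by arm. The AE tables in SAP 7.1, by preferred term and treatment group, largely provide this already.
3. Show TICI grade and post-randomization or rescue thrombolytic use in a separate display, labelled as post-randomization and descriptive. If a causal answer on thrombolytic use is wanted, it needs its own stated estimand as an intercurrent event.
4. Align Table 9-1 and SAP 6.4 when the SAP is brought up to the current protocol.

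The cost is a few lines of wording in both documents and fewer rows in the forest plot. No change to data collection, sample size or the testing sequence is needed.
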